##### **12.1.2.2      Other safety variables**

The other safety variables include changes in laboratory parameters (ie, hematology, clinical chemistry, endocrinology, and urinalysis), 12-lead ECG measurements, vital sign measurements (blood pressure and pulse rate), physical and neurological exam findings, body weight, height, calculated BMI, and Tanner Stage (if applicable). The actual measurement and its change from Baseline (SP847 [or other primary study as applicable] Visit 1) or the Screening Visit (for subjects who entered directly into SP848) will be analyzed descriptively and presented by visit. In addition, shift tables may be used to evaluate the number and percentage of subjects having a different post-Baseline status when compared with their Baseline status.

The shift from Baseline to the subject's last visit at which a physical and/or neurological examination was performed post-Baseline will be summarized by category.

Laboratory, ECG, and vital signs data outside of the respective reference ranges will be listed and highlighted.

Changes in behavior and development from Baseline as measured using the Achenbach CBCL for children 18 months and older (CBCL/1½-5 and CBCL/6-18) and Bayley-III scales for children <18 months of age will be summarized descriptively and presented by visit. Changes in cognitive function as measured using the BRIEF-P/BRIEF will be summarized by descriptive statistics at each visit. Baseline is defined as Visit 1 for subjects from SP847 or other epilepsy studies. Baseline values for subjects who enroll directly into SP848 will be taken from the Screening Visit.

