## 1 SUMMARY

SP848 is an open-label study to obtain long-term safety, tolerability, and pharmacokinetic (PK) data in children with epilepsy (partial-onset seizures and other pediatric epilepsy syndromes) treated with lacosamide (LCM) oral solution (syrup) or LCM tablets as adjunctive therapy. In addition, the study is designed to obtain preliminary efficacy data on seizure frequency during long-term exposure. The study will also provide continued availability of LCM to subjects who have completed the SP847 epilepsy study and to subjects who have discontinued from SP847 due to a dose reduction or status epilepticus, and who, in the investigator's opinion, would benefit from long-term administration of LCM.

SP848 was originally designed as an open-label extension study for pediatric subjects in SP847 with partial-onset seizures. SP848 is now amended to be open to subjects who participate in other LCM pediatric clinical studies, including partial-onset seizures and other epilepsy syndromes. SP848 includes subjects  $\geq 1$  month to  $\leq 18$  years of age since subjects who complete SP847 or another applicable LCM pediatric epilepsy study in subjects  $<18$  years of age may have aged to 18 years old by the time they complete that study and enroll in SP848.

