In addition, at selected sites, beginning with Protocol Amendment 4, up to approximately 100 eligible pediatric subjects  $\geq 4$  years to  $\leq 17$  years of age with partial-onset seizures (deemed appropriate for treatment with adjunctive LCM) who have not previously participated in a LCM clinical study will be permitted to enroll directly into SP848. Beginning with local Protocol Amendment 5.2 for sites in Japan, approximately 46 eligible pediatric subjects  $\geq 4$  years to  $\leq 17$  years of age with partial-onset seizures who have not previously received LCM will directly enroll at approximately 9 sites in Japan. Beginning with local Protocol Amendment 5.4 for sites in China, approximately 60 additional eligible pediatric subjects with partial-onset seizures aged  $\geq 4$  years to  $\leq 17$  years, who have not previously participated in a LCM clinical study, will enroll directly into SP848. The purpose of enrolling these subjects directly into SP848 is to obtain sufficient long-term safety exposures in the age range of  $\geq 4$  years to  $\leq 17$  years of age; the long-term safety data will be included in planned regulatory submissions for LCM as adjunctive therapy for partial-onset seizures in pediatric subjects  $\geq 4$  years to  $\leq 17$  years of age with epilepsy.

Protocol Amendment 6 allows up to approximately 75 additional eligible pediatric subjects with epilepsy who participated in EP0060 to enroll into SP848. Protocol Amendment 8 allows an enrollment increase from 75 to 100 eligible pediatric subjects  $\geq 1$  month to  $\leq 17$  years of age with epilepsy who participated in EP0060 to enroll in SP848 in order to reflect EP0060's inclusion of subjects down to 1 month of age. In addition, subjects already enrolled in SP848 may participate in EP0060, if eligible, and then resume participation in SP848. These subjects may either voluntarily choose to have an iv LCM infusion even though they are capable of taking oral LCM or require iv LCM infusion due to a medical reason or procedure (ie, unable to take oral LCM).

Approximately 200 subjects who may participate in other LCM pediatric clinical studies in epilepsy will be eligible to participate in SP848. In total, up to approximately 400 subjects may be eligible to participate in SP848.

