Three double-blind, placebo-controlled, multicenter studies (SP667, SP754, and SP755) in 1308 adult subjects, aged 16 to 70 years, established the efficacy of oral LCM as adjunctive therapy (1 to 3 concomitant AEDs) in subjects with difficult to control partial-onset seizures. In these studies, LCM was initiated at a dose of 100mg/day (in 2 divided doses) and escalated to the randomized dose (200mg/day, 400mg/day, or 600mg/day) in 100mg/day per week increments.

When oral LCM was administered as adjunctive therapy at doses up to 600mg/day in the 3 double-blind, placebo-controlled, multicenter studies in subjects with partial-onset seizures, the most frequently reported treatment-emergent adverse events (TEAEs) were central nervous

system- and gastrointestinal-associated events. A dose relationship was seen for the most frequently reported common TEAEs, including dizziness, nausea, and diplopia. The nature and frequency of adverse events (AEs) were comparable to adjunctive therapy with other marketed AEDs. Safety evaluations support the further development of LCM as an AED.

SP847 was an open-label, dose-titration, safety, tolerability, and PK study to evaluate LCM as adjunctive therapy in children with uncontrolled partial-onset seizures. The study completed on 26 Aug 2014. Forty-seven subjects (aged 1 month to 17 years) with uncontrolled partial-onset seizures on a stable dose regimen of at least 1 but no more than 3 AEDs were enrolled and treated during the study. The study consisted of a Screening Phase, a Treatment Phase, and an End-of-Study Phase. The duration of treatment for an individual subject was up to approximately 13 weeks.

SP848 is an open-label study to obtain long-term safety, tolerability, and pharmacokinetic (PK) data in children with epilepsy (partial-onset seizures and other pediatric epilepsy syndromes) treated with LCM oral solution (syrup) or LCM tablets as adjunctive therapy. In addition, the study is designed to obtain preliminary efficacy data on seizure frequency during long-term exposure. The study will also provide continued availability of LCM to subjects who have completed the SP847 epilepsy study and to subjects who have discontinued from SP847 due to a dose reduction or status epilepticus, and who, in the investigator's opinion, would benefit from long-term administration of LCM.

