#### **4.2.1.2 Other safety variables**

The other safety variables are:

- Hematology, blood chemistry, endocrinology, and urinalysis parameters
- 12-lead electrocardiograms (ECGs)
- Vital sign measurements (blood pressure and pulse)
- Physical and neurological examination findings
- Body weight, height, and calculated body mass index (BMI)
- Tanner Stage (if applicable)
- Achenbach Child Behavior Checklist (CBCL) at Baseline for children 18 months and older (CBCL/1½-5 and CBCL/6-18) assessing behavior
- Bayley-III scales at Baseline for children  $<18$  months of age at time of enrollment (applicable only to subjects enrolled in English-speaking countries)
- Cognitive function assessments (Behavior Rating Inventory of Executive Function® [BRIEF®]/BRIEF®-Preschool Version [BRIEF®-P]) (if applicable)
- LCM palatability and ease of use questionnaire

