#### 4.5 Expected duration of the study

The maximum duration of LCM administration for an individual subject will be approximately 2 years or until approval of the marketing application (for Japan only), whichever comes first.

The start of the study is defined as the first visit of the first subject entering the study. The end of the study is defined as the date of the last visit of the last subject in the study.

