### **5.16 Visit 13/Termination Visit (Week 96)**

At the completion of the study, investigators should discuss treatment options with the subject and/or their parent/legal guardian to best manage the subject's epilepsy. Taper of LCM may not be required for some subjects who complete the study depending on the treatment option selected by the investigator in consultation with the subject and/or parent/legal guardian. These subjects should complete Visit 13/Termination Visit and then complete the Safety Follow-Up telephone contact 28 to 35 days after Visit 13/Termination Visit. The Final Visit is not required for subjects who complete the study and who do not undergo taper of LCM. The Safety Follow-Up Visit and the Safety Follow-Up telephone contact are not required for subjects who participate in EP0151 or EP0152.

Subjects who complete the study and discontinue use of LCM (as determined by the investigator in consultation with the subject and/or parent/legal guardian) should taper LCM gradually as described in [Section 4.4.1.3](#). These subjects should complete Visit 13/Termination Visit, followed by the Final Visit which occurs 2 weeks after the final dose of study medication, and then the Safety Follow-Up telephone contact which occurs 28 to 35 days after the last dose of LCM.

Assessments for Visit 13/Termination Visit (Week 96) are the same as those described for Visit 5 (Week 20), in [Section 5.8](#), with the following exceptions for all sites: the laboratory blood sample is collected only for clinical chemistry and hematology (ie, no endocrinology), a 12-lead ECG (2 interpretable recordings approximately 20 to 30 minutes apart prior to vital signs assessment and collection of blood sample) is conducted, a Tanner Stage assessment is conducted (if applicable), an Achenbach CBCL is conducted, Bayley-III scales are conducted, BRIEF-P/BRIEF and PedsQL scores are obtained, and the palatability and ease of use questionnaire is completed. In addition to the noted differences, a PK sample is routinely drawn at sites in Japan (removed for all other sites).

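### Weight, height and BMI are summarised only as actual value and change from Baseline, so slowed growth would still read as a gain; age- and sex-standardised scores should be added

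*Protocol*

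**What the plan says.** Section 4.2.1.2 names "Body weight, height, and calculated body mass index (BMI" among the other safety variables. Section 12.1.2.2 places these three in one list with laboratory values, ECG, vital signs, examination findings and Tanner Stage, and gives all the measurements one treatment. It reads "body weight, height, calculated BMI, and Tanner Stage (if applicable). The actual measurement and its change from Baseline", and these "will be analyzed descriptively and presented by visit". Baseline is Visit 1 of the primary study, or the SP848 Screening Visit for direct enrollers.

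No standardised score, percentile, growth velocity or reference population is named for growth. Shift tables are optional, and no categories are given for weight, height or BMI. The out-of-range listing covers laboratory, ECG and vital signs data, and vital signs are defined as blood pressure and pulse.

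On the population, Section 1 opens EP0060 entry "in order to reflect EP0060's inclusion of subjects down to 1 month of age". It also explains the upper limit of 18 years by subjects who "may have aged to 18 years old by the time they complete that study and enroll in SP848". Section 4.4.3 confirms that nobody is randomised. On duration, the last scheduled visit is at Week 96 (Section 5.16), and Section 4.5 states that "The maximum duration of LCM administration for an individual subject will be approximately 2 years".

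**The concern.** In an adult study, change from Baseline in weight has a natural benchmark of zero. In growing children it does not: height and weight rise with age on or off drug, and the expected value of BMI also depends on age and sex. With no control arm, the only available benchmark is the growth expected for a child of that age and sex, and the stated analysis does not use it.

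Two things follow. First, a child who grows more slowly than expected still contributes a positive change, so the sign of the mean says little. Second, the mean at a visit depends on how old the contributing subjects are, and that mix can differ between visits. Direct enrollers are 4 to 17 years old while EP0060 entrants may be 1 month old. Subjects in Japan may stop at marketing approval (Section 4.5). Subjects who discontinue contribute only the visits they attended, and nothing is imputed (Section 12.1.5).

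At stake is whether two years of paediatric growth data can be read at all as safety information. The protocol takes an interest in physical development, since it collects Tanner Stage and endocrinology, and it already scores behaviour on the CBCL against a normative sample (Section 8.4.7).

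**Working it through.** The protocol gives no figure on this point, so there is nothing to reproduce. The check is of the text, followed by an illustration.

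**1. Is there a growth benchmark anywhere in the current text?**
- Sections 4.2.1.2 and 12.1.2.2: actual value and change only.
- Shift tables: optional, with no growth categories.
- Out-of-range listing: does not reach weight, height or BMI.
- Section 12.1: more detail is deferred to the SAP, but no growth standardisation is announced.

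So none is stated.

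**2. Over what time does change accrue?** Years = weeks × 7 / 365.25.
- From Visit 1 to Week 96: 96 × 7 / 365.25 = 1.84 years.
- Direct enrollers, from Screening: up to 2 weeks of screening + about 6 weeks of titration + 96 = 104 weeks = 1.99 years.
- SP847 entrants: Section 2 says of SP847 that "The duration of treatment for an individual subject was up to approximately 13 weeks", so an upper limit is 13 + 96 = 109 weeks = 2.09 years. Section 5.3 puts SP848 Visit 1 at SP847 Day 28 to 42 for completers, so for most the lead-in would be nearer 4 to 6 weeks.

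The figures below use 96 weeks, which understates the interval.

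**3. Does slowed growth change the sign?** Height change = v × (1 − s) × 1.84, with velocity v and proportional slowing s. Both are assumptions for illustration; neither is in the documents. Results are in cm.

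| v (cm/year) | s = 0 | s = 10% | s = 20% | s = 30% |
|---|---|---|---|---|
| 4 | 7.4 | 6.6 | 5.9 | 5.2 |
| 6 | 11.0 | 9.9 | 8.8 | 7.7 |
| 8 | 14.7 | 13.2 | 11.8 | 10.3 |
| 12 | 22.1 | 19.9 | 17.7 | 15.5 |

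Every entry is positive. At 20% slowing the shortfall is 4 × 0.20 × 1.84 = 1.5 cm to 12 × 0.20 × 1.84 = 4.4 cm. The spread in normal growth across the assumed velocities is 22.1 − 7.4 = 14.7 cm.

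**4. Does the age mix move the mean?** Assume 10 cm/year in young and 5.5 cm/year in older children, with a share f of young children: mean = [10f + 5.5(1 − f)] × 1.84.
- f = 5%: 5.725 × 1.84 = 10.5 cm.
- f = 35%: 7.075 × 1.84 = 13.0 cm.
- f = 35% with 15% slowing in every child: 13.0 × 0.85 = 11.1 cm.

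Under these assumptions a uniformly slowed group with more young children shows a larger mean gain (11.1 cm) than an unaffected group with few (10.5 cm). The shares are invented, since the protocol gives no expected age distribution. The example shows the direction of the problem, not its size in this study.

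**The case against.** The best counter-argument is that Section 12.1.2.2 gives one generic sentence for many variables, that Section 12.1 leaves detail to the SAP, and that derivation of growth scores is usual SAP content. The sentence does not forbid adding them. That stands in part: the SAP may already do so, and the fix allows for it. But the protocol has stated a scale for these variables, and followed as written that scale has no growth benchmark.

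Several stronger readings are tempting, and the documents do not support them.
- A reader might infer that the planned analysis cannot show an effect of LCM on growth and that standardised scores would. In a single-arm study with changing concomitant AEDs, neither scale attributes a shift to LCM. A zero expected change in score also assumes that these children track the reference population, which nothing in the protocol establishes.
- A reader might infer that all ages will be pooled in one table. The protocol names no age groups, but it does not say it will pool.
- A reader might infer that the planned summaries are useless. Gross weight loss would still show, and by-visit weight matters in a study dosed in mg/kg.

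It is also fair that growth is neither an objective nor a primary safety variable, that the study is descriptive, and that a growth problem noticed clinically could be reported as an adverse event. These limit the importance of the point, not its correctness.

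**Conclusion.** The point holds in a limited form. As written, Section 12.1.2.2 gives only the actual value and its change for weight, height and BMI. In growing children followed to Week 96 without a control arm, slowed growth still appears as a gain, and the mean depends on the ages of those present at each visit. That conclusion rests on the text and on the fact that children grow. The size is illustrative: under the assumed velocities, a 20% slowing hides a shortfall of 1.5 to 4.4 cm inside a positive change of 5.9 to 17.7 cm. No figure in the protocol is wrong, and no primary or secondary conclusion is affected. It is a cheap improvement.

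**What to change.** In Section 12.1.2.2, keep the by-visit summaries of actual values and change. Add:
- the change from Baseline in age- and sex-standardised height, weight and BMI scores, by visit, against a named reference;
- the number and percentage of subjects crossing a predefined band of those scores.

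If the SAP already plans these, bring the protocol text into line with it.

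The cost is programming. Weight and height are scheduled at Screening for direct enrollers and at Visits 1 to 13, so no new visits or measurements are needed. The downsides are that a reference must be chosen for a multi-country population that includes Japan and China, and that the report must say that a shift shows departure from that reference and does not by itself attribute it to LCM.

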Lacosamide (LCM, Vimpat®, SPM 927, [R]-2-acetamido-N-benzyl-3-methoxypropionamide) belongs to a novel class of functionalized amino acids. It has minimal protein binding and effect on cytochrome P450 enzyme system function (reducing the risk of drug-drug interactions), high oral bioavailability, and a half-life of approximately 13 hours (in adults), which allows a twice daily (bid) dose regimen. It also displays dose-proportional PK following administration over a range of doses up to 800mg in adults.

Lacosamide (200mg/day to 400mg/day) is approved and indicated as adjunctive therapy in the treatment of partial-onset seizures with or without secondary generalization in adult and adolescent (16 to 18 years of age) patients with epilepsy and was first approved in Aug 2008 by the European Commission. Lacosamide is available in tablet (50mg, 100mg, 150mg, and 200mg) and syrup (10mg/mL) oral formulations as well as solution for infusion (10mg/mL) formulation for use as temporary iv replacement when oral administration is not feasible. Lacosamide (200mg/day to 400mg/day) was approved in the US in Oct 2008 as adjunctive therapy and in Aug 2014 as monotherapy in the treatment of partial-onset seizures in patients 17 years of age and older. Initiation of adjunctive LCM treatment with a single loading dose of LCM 200mg (oral tablets, syrup, or iv infusion) followed 12 hours later by a LCM 100mg twice daily (200mg/day) maintenance dose regimen was also approved by the European Commission in Nov 2012. Use of a LCM 200mg loading dose for initiation of initial LCM monotherapy, conversion to LCM monotherapy, or adjunctive therapy was approved in the US in Aug 2014.

The oral solution (syrup) is a formulation suitable for administration to children. Bioequivalence has been shown between the tablet and oral solution (syrup) formulations, comparing 2 tablets of LCM 100mg and the oral solution (syrup) containing LCM 200mg, after single-dose administration in healthy subjects. The PK of LCM and its major metabolite, SPM 12809 (O-desmethyl-LCM), in plasma, urine, and saliva were identical or very similar after single oral doses of LCM 200mg administered as tablets or as oral solution (syrup).

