#### 4.4.1.4 Study completion

At the completion of the study, investigators should discuss treatment options with the subject and/or their parent/legal guardian to best manage the subject's epilepsy. Taper of LCM may not be required for some subjects who complete the study depending on the treatment option selected by the investigator in consultation with the subject and/or parent/legal guardian. These subjects should complete Visit 13/Termination Visit and then complete the Safety Follow-Up telephone contact 28 to 35 days after Visit 13/Termination Visit. The Final Visit is not required for subjects who complete the study and who do not undergo taper of LCM. The Safety Follow-Up Visit and the Safety Follow-Up telephone contact are not required for subjects who participate in EP0151 or EP0152.

Subjects who complete the study and discontinue use of LCM (as determined by the investigator in consultation with the subject and/or parent/legal guardian) should taper LCM gradually as described in Section 4.4.1.3. These subjects should complete Visit 13/Termination Visit, followed by the Final Visit which occurs 2 weeks after the final dose of study medication, and then the Safety Follow-Up telephone contact which occurs 28 to 35 days after the last dose of LCM.

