## 5.17 Early Termination Visit

Subjects who withdraw from the study prematurely must complete an Early Termination Visit.

At the time of withdrawal from the study, investigators should discuss treatment options with the subject and/or their parent/legal guardian to best manage the subject's epilepsy. Taper of LCM may not be required for some subjects who withdraw from the study prematurely, depending on the treatment option selected by the investigator in consultation with the subject and/or parent/legal guardian. These subjects should complete the Early Termination Visit and then complete the Safety Follow-Up telephone contact 28 to 35 days after the Early Termination Visit. The Final Visit is not required for subjects who withdraw from the study prematurely and who do not undergo taper of LCM.

Subjects who withdraw from the study prematurely and discontinue use of LCM (as determined by the investigator in consultation with the subject and/or parent/legal guardian) should taper LCM gradually as described in Section 4.4.1.3. These subjects should complete the Early Termination Visit, followed by the Final Visit which occurs 2 weeks after the final dose of study medication, and then the Safety Follow-Up telephone contact.

The following will be performed at the Early Termination Visit:

- Concomitant medication assessment
- Concomitant AEDs assessment
- Complete physical examination
- Complete neurological examination
- 12-lead ECG (2 interpretable recordings approximately 20 to 30 minutes apart prior to vital signs assessment and collection of blood samples)
- Vital signs assessment (blood pressure and pulse)
- Body weight and height
- Blood sample for clinical chemistry, hematology, and endocrinology
- Blood sample for LCM and concomitant AED plasma concentrations (at any time post-dosing with LCM)
  - Under any circumstance for an ETV during Year 1
  - If possible, if the early termination during Year 2 is due to a SAE and the event is ongoing
- Urine sample for urinalysis
- Serum pregnancy test for females of childbearing potential
- Tanner Stage assessment (if applicable)
- Clinical Global Impression of Change

- Caregiver Global Impression of Change
- LCM return/compliance
- Subject diary assessment
- C-SSRS
- Achenbach CBCL to be completed by the parent(s)/legal representative(s) (CBCL/1½-5 for children from 18 months to 5 years 11 months and CBCL/6-18 for children 6 years and older)

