## 5.19 Final Visit

Subjects who complete the study or withdraw prematurely from the study, and who discontinue use of LCM (ie, taper), should complete the Final Visit 2 weeks after the final dose of study medication. The Final Visit is not required for subjects who participate in EP0151 or EP0152.

During the Final Visit, the following will be performed:

- Concomitant medications assessment
- Concomitant AEDs assessment
- Complete physical examination
- Complete neurological examination
- 12-lead ECG (2 interpretable recordings approximately 20 to 30 minutes apart prior to vital signs assessment and collection of blood samples)
- Vital signs assessment (blood pressure and pulse)
- Body weight and height assessment
- Blood sample for clinical chemistry, hematology, and endocrinology

- Urine sample for urinalysis
- Serum pregnancy test for female subjects of childbearing potential
- LCM return/compliance
- Subject diary assessment
- C-SSRS
- Adverse event reporting
- Health care resource use

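### The physical/neurological examination shift ends at the last examination of any kind, so one table mixes off-drug results (children who taper off LCM) with on-drug results (children who continue)

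*Protocol*

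**What the plan says.** Section 12.1.2.2 of the protocol commits to one shift summary for examinations. Its starting point is Baseline, and its endpoint is given as follows: "last visit at which a physical and/or neurological examination was performed post-Baseline will be summarized by category". Nothing limits the endpoint to visits on treatment. For the other variables in that section, shift tables are only optional.

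The visit sections decide which examination comes last:

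- **Children who discontinue LCM.** Section 5.19 says that they "should complete the Final Visit 2 weeks after the final dose of study medication", and its list of procedures includes a complete physical examination and a "Complete neurological examination". Under Section 5.17, early withdrawals who stop LCM first have an end-of-treatment visit, which is described as "followed by the Final Visit which occurs 2 weeks after the final dose of study medication, and then the Safety Follow-Up telephone contact". Sections 4.4.1.4 and 5.16 do the same for completers after Visit 13.
- **Completers who continue LCM.** Section 4.4.1.4: "The Final Visit is not required for subjects who complete the study and who do not undergo taper of LCM".
- **Early withdrawals without taper.** Section 5.17: "The Final Visit is not required for subjects who withdraw from the study prematurely and who do not undergo taper of LCM".
- **Children moving to a follow-on study.** Section 5.19: "The Final Visit is not required for subjects who participate in EP0151 or EP0152".

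Complete physical and neurological examinations are also scheduled at Visit 13 and at the Early Termination Visit. A child who tapers therefore has an examination before the taper and another after washout.

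**The concern.** A shift from Baseline to a single last value is usually read as the child's status at the end of treatment. Here the last value is taken in a different drug state depending on whether the child stopped LCM. The category counts then combine two questions: what examinations look like on long-term LCM, and what they look like after LCM has been withdrawn.

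This matters more for neurological findings than for most variables. Section 2 describes central nervous system effects as among the most frequent with LCM, and names dizziness and diplopia among those related to dose. If a child has a reversible sign at the Early Termination Visit, the rule replaces that result with one obtained after washout. Conversely, a sign that first appears after LCM is stopped enters a table that a reader would take to describe LCM exposure.

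**Working it through.** **Step 1. Trace the last scheduled examination by exit route** (Sections 4.4.1.4, 5.16, 5.17 and 5.19).

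| Exit route | Last scheduled examination | Drug state |
|---|---|---|
| Completer, tapers off LCM | Final Visit | 2 weeks off |
| Early withdrawal, tapers off LCM | Final Visit | 2 weeks off |
| Completer, continues LCM | Visit 13 | normally on |
| Early withdrawal, no taper | Early Termination Visit | normally on |
| Enters EP0151 or EP0152 | Visit 13 or Early Termination Visit | normally on |

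One route is unclear. The Final Visit is tied to discontinuing LCM with taper, but taper supplies are dispensed only above a dose threshold (Sections 5.16 and 5.17). Whether a child stopping from a lower dose attends the Final Visit cannot be settled from the text.

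**Step 2. Check that the Final Visit is off drug.** The only half-life given is about 13 h in adults (Section 2).

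- Interval: 14 days × 24 h = 336 h.
- Half-lives: 336 / 13 = 25.8.
- Fraction remaining: 2^(−25.8), about 1.7 × 10⁻⁸.

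No plausible paediatric difference in half-life would change the conclusion. This shows that the drug is gone. It does not show that any finding has reversed.

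**Step 3. Illustrate how many abnormalities could leave the table.** The plan states no figure to reproduce. Let N be the number of children, p the share with an abnormality at the last on-drug examination (taken as equal in stoppers and continuers), q the share who have a Final Visit, and r the share of abnormalities resolved by then.

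Number missing from the shift = N × p × q × r.

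N = 400 is the enrolment ceiling in Section 12.2. The values p = 10%, q = 20% to 50% and r = 0% to 100% are assumptions, because the documents give none of them. Then N × p = 40 children have such an abnormality, and the number missing is:

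| r | q = 20% | q = 35% | q = 50% |
|---|---|---|---|
| 0% | 0 | 0 | 0 |
| 25% | 2 | 3.5 | 5 |
| 50% | 4 | 7 | 10 |
| 100% | 8 | 14 | 20 |

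The range is 0 to 20 of 400, or 0 to 5 percentage points (20 / 400 = 5%). Among children with a Final Visit, the share of on-drug abnormalities lost equals r, which can lie anywhere from none to all. The calculation ignores findings that first appear after stopping, which would add to the count.

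**The case against.** The strongest reply is that nothing leaves the safety analysis. Section 12.1.2.2 lists physical and neurological findings among the variables presented by visit, so Visit 13 and Early Termination Visit results should appear separately from the Final Visit. Clinically relevant problems are also reported as adverse events. TEAE incidence and withdrawal due to TEAEs are primary safety variables (Section 4.2.1.1), and Section 12.1.2.1.1 counts events up to 30 days after the last dose. A child who stops because of dizziness is counted there whatever the Final Visit shows. This stands, and it limits the harm to one table. It does not repair that table. Early terminations fall at any week, and the shift is the summary that gives one end result per child.

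A second reply is that end-of-study status is a legitimate thing to describe. It is, but here that status is taken off drug for some children and on drug for others.

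A third is that the Early Termination Visit need not be on drug or at full dose. Section 5.4 lets doses be cut by telephone before a visit, and Section 4.3.3.1 requires immediate discontinuation in some liver cases. This also stands, and it is a reason to define the endpoint by drug status and not by visit name alone.

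Finally, Section 12.1 leaves further detail to the Statistical Analysis Plan, which was not available for this point. Visit windows commonly belong there. But the last-visit rule is not left open: the protocol states it.

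**Conclusion.** The point holds as a flaw in one descriptive summary. The endpoint of the examination shift is off drug for children who taper off LCM and normally on drug for the rest, and the rule does not separate them. Abnormalities that reverse after stopping can leave the table, and abnormalities that arise after stopping can enter it. The size cannot be derived from the documents and may be near zero. The 0 to 5 points above rest wholly on assumed rates. No hypothesis test, sample size or primary variable is touched. The grade is minor to moderate.

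A reader might infer more: that on-treatment abnormalities disappear from the study, that the loss falls on exactly the children who could not tolerate LCM, or that the table is necessarily biased towards no change. The documents support none of these. Persistent findings remain in the shift, and findings that resolve still appear in the by-visit summaries. The group with a Final Visit includes completers who choose to stop. Findings that emerge after withdrawal would move the counts the other way, so the direction of the net effect is not fixed.

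**What to change.** In Section 12.1.2.2, define the examination shift as Baseline to the last physical or neurological examination performed while the child was on LCM: Visit 13/Termination Visit, the Early Termination Visit, or the last earlier on-treatment visit. Decide whether an examination counts as on LCM by comparing its date with the date of the last dose, so that an Early Termination Visit held after dosing has stopped is not counted. Present the Final Visit examination as a separate post-treatment shift, restricted to children who have one and showing their number.

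The cost is one sentence in the protocol, carried into the Statistical Analysis Plan, and one additional table. Every examination needed is already scheduled, so sites and children carry no added burden.
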